### **5. AMENDMENTS AND UPDATES**

#### **5.1 Changes from protocol analysis**

Additional modifications from the CTP made in this SEAP:

- It was stated in CTP to exclude patients with missing values. Missing values will be treated in a different way according to their nature. Missing values due to Intercurrent Event (IE) are taken care at the estimands definitions, on the other hand, missing values not related to IE will be multiple imputed if missingness is greater than 25% for a specific variable.
- It was suggested in the CTP, [REDACTED]  
[REDACTED]
- To assess the potential associations between patient characteristics, treatment, preference [REDACTED]ing

to health status assessed with CAT will not be assessed via univariate methods, however the applicable [REDACTED] are included to the statistical models in the primary and the first secondary endpoint analysis.

[REDACTED]

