## **8.2 Outcomes**

### **8.2.1 Primary outcomes**

[figure not shown]
The primary outcome of this NIS will be the mean change in patients' quality of life (QoL) according to the total score of COPD Assessment Test (CAT) within three months after the switch from Spiriva® Handihaler® to Spiolto® Respimat® according to the daily clinical practice.

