### 8.3 Covariates

The following variables will be considered, among others, as covariates and will be examined in terms of their association with the primary outcome measure.

- Patient' s age at baseline (<65 years,  $\geq 65$  years)
- Sex (female, male)
- Obesity (i.e. BMI  $\geq 30$  kg/m^2) (yes, no)
- Smoking habits (current smoker, past smoker).
- Packyears
- Gold group (A, B, C and D).

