#### 11.2.1 Analysis of primary outcome.

11.2.1.1 Mean change in patients' quality of life (QoL) according to the total score of COPD Assessment Test (CAT) within three months after the switch from Spiriva® Handihaler® to Spiolto® Respimat®.

The primary estimand is defined as follows:

- A. Population: Is defined through inclusion/exclusion criteria of the study protocol to reflect the target population.
- B. Variable: Continuous variable response.

- C. Intercurrent Event (IE): Include death, drop-out due to any adverse event (AE) and treatment discontinuation. For patients experiencing an IE, the most extreme unfavourable value will be assigned (CAT score at 3 Months equals to 40).
- D. Population level summary: The change from Baseline of total CAT score within 3 Months.

Mixed model for repeated measurements (MMRM) assuming random missingness will be fitted. The dependent variable will be the CAT score at each visit. Visit, GOLD group, smoking habits, packyears, sex, age, and comorbidities appearing at a rate greater than 5% will be entered as covariates. Patients will be fitted at random and an unstructured covariance matrix will be used, allowing adjustment for correlations between study visits within the study patients. The Kenward- Roger degrees of freedom approximation will be used in the model (ddfm=kr).

Summaries of the estimated mean change from baseline of CAT score at 3 Months will be provided with 95% confidence interval. Model information will be provided as footnote under the corresponding table.

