### **11.2.2 Analysis of Secondary outcomes.**

#### **11.2.2.1 Change in the proportion of patients with COPD Assessment Test (CAT) $\geq 10$ (representing impaired health status) within three months after the switch**

Estimand:

- A. Population: Is defined through inclusion/exclusion criteria of the study protocol to reflect the target population.
- B. Variable: Binary variable response. Response is defined as having CAT score  $\geq 10$ .
- C. Intercurrent Event (IE): Include death, drop-out due to any adverse event (AE) and treatment discontinuation. For patients experiencing an IE, the most extreme unfavourable value will be assigned (patient CAT score  $\geq 10$ ).
- D. Population Level Summary: Odds ratio of response within 3 Months.

This endpoint will be analysed with a logistic GEE model with CAT response as dependent variable. Visit, GOLD group, smoking habits, packyears, sex, age, and comorbidities appearing at a rate greater than 5% will be entered as covariates and unstructured covariance matrix will be used.

Summaries of the estimated OR will be provided with 95% confidence interval. Model information will be provided as footnote under the corresponding table.

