**TABLE 6.2.1 CHANGE FROM BASELINE TOTAL CAT SCORE ESTIMATES DURING THE TRIAL BASED ON [REDACTED]**

Visit	LS Mean	95%CI
Month 3 Change from Baseline		
Covariate 1...n		

Footnote: CAT: COPD Assessment Test. LS: Least Square

Footnote: adjusted for covariates

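### In the readable SAP, the covariate terms of the CAT models estimate differences in CAT level, not the association with CAT change that section 8.3 plans to examine

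*SAP*

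**What the plan says.** - SAP 8.3 lists age, sex, obesity, smoking, pack-years and GOLD group and states: "The following variables will be considered, among others, as covariates and will be examined in terms of their association with the primary outcome measure". SAP 8.2.1 fixes that measure: "The primary outcome of this NIS will be the mean change in" quality of life by total CAT score.
- SAP 5.1, partly blacked out, says that associations with CAT health status will not be assessed by univariate methods and that the applicable terms "are included to the statistical models in the primary and the first secondary endpoint analysis".
- SAP 11.2.1.1, the primary mixed model: "The dependent variable will be the CAT score at each visit". Its terms: "Visit, GOLD group, smoking habits, packyears, sex, age, and comorbidities appearing at a rate greater than 5% will be entered as covariates". The covariance is unstructured over the visits.
- SAP 11.2.2.1, the first secondary outcome: "This endpoint will be analysed with a logistic GEE model with CAT response as dependent variable". The covariate list is the same.
- Neither section names a visit-by-covariate term. Obesity is in 8.3 but in neither model.
- SAP Annex 1, Table 6.2.1 is titled "CHANGE FROM BASELINE TOTAL CAT SCORE ESTIMATES DURING THE TRIAL BASED ON" (the basis is blacked out). Under the month 3 change row it has rows for covariates 1 to n, in columns for the LS mean and 95% CI, and a footnote that the results are covariate-adjusted. Table 7.2.1 has the same layout for odds ratios.
- Protocol 9.1, Table 1, footnote 2: GOLD group is calculated in the eCRF from exacerbation history, mMRC and CAT.

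**The concern.** The question in 8.3 is who changes more after the switch. A model of the score at each visit, with covariates entered once and not crossed with visit, answers a different question: who has the higher CAT score over the two visits taken together. The term list does not use the words main effects, but that is its plain reading when no interaction is named.

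The table layout makes the mix-up easy. A row for sex or smoking directly below the month 3 change, under a change-from-baseline title, invites the reader to take it as an effect on improvement. A group that starts sicker and improves more could then be read as doing worse, and a characteristic with a real difference in change could look irrelevant.

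**Working it through.** **1. The plan's own figure.** The concern turns on no stated number, but Protocol 9.5 supplies the SD of paired differences (9.0) and the evaluable N (1310). The smallest n with P(t(0.975, n−1) × s/√n ≤ 0.5) ≥ 0.90, with s² following 81 × χ²(n−1)/(n−1), is 1310 (probability 0.9007). It reproduces.

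**2. What a covariate coefficient estimates.** Let a binary characteristic shift CAT by L at baseline and by L + D at month 3, so that D is the difference in change. In the model with visit and covariate only, the coefficient is a weighted average of the two shifts:

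coefficient = L + w₂ × D, with w₂ = (s₁² − c)/(s₁² + s₂² − 2c) and c = (s₁² + s₂² − 81)/2.

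The visit SDs are not in the documents; 8/8 and 8/10 are assumed.
- 8/8: c = (64 + 64 − 81)/2 = 23.5; w₂ = 40.5/81 = 0.50.
- 8/10: c = (64 + 100 − 81)/2 = 41.5; w₂ = 22.5/81 = 0.278.

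Simulation used N = 1310, complete data, a 50/50 covariate and 200 runs per scenario. L and D are illustrative. Paired values are for SDs 8/8 and 8/10.

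| L | D (true difference in change) | Coefficient by formula | Coefficient simulated | Visit-by-covariate term simulated |
|---|---|---|---|---|
| 6 | 0 | 6.0 / 6.0 | 6.01 / 5.97 | −0.03 / −0.05 |
| 1 | −2 | 0.0 / 0.44 | 0.01 / 0.43 | −2.07 / −2.01 |
| 0 | −2 | −1.0 / −0.56 | −1.00 / −0.58 | −2.02 / −2.03 |
| 6 | −4 | 4.0 / 4.89 | 4.00 / 4.86 | −4.05 / −4.00 |

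The first row shows a large coefficient with no association with change. The second shows an association with change that nearly vanishes. The fourth shows a positive coefficient for the group that improves by 4 points more. The interaction recovers D each time.

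**3. What happens to the overall change.** A covariate with the same value at both visits cancels from each within-patient difference. With complete data, the visit estimate in the linear model equalled the raw paired mean change to better than 1e-12 in every run. This has three limits:
- It does not carry over to the logistic GEE, because odds ratios are not collapsible. With one fixed binary covariate and complete data, the simulated visit odds ratio moved from 0.55 to 0.50 (covariate log odds ratio 1.5) and from 0.63 to 0.51 (log odds ratio 2.5).
- It does not apply with incomplete data.
- It does not apply to covariates that vary over time. With a time-varying indicator of CAT ≥ 10 as a stand-in for GOLD (SDs 8/8, baseline mean 14), the visit estimate moved from −1.06 to −0.38.

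**4. Precision of an interaction.** For a 50/50 covariate at N = 1310: SE = 9.0 × √(1/655 + 1/655) = 0.497; 1.96 × 0.497 = 0.97, so about ±1 CAT point.

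**5. Why GOLD needs separate treatment.** Take SDs 8/8, normal scores and no true difference in change. The slope of change on baseline is 23.5/64 − 1 = −0.633. Split at baseline CAT 10; the group means lie 8φ(z)/Φ(z) above and 8φ(z)/(1 − Φ(z)) below the overall mean, with z = (mean − 10)/8.
- Mean 14: 18.07 against 4.87; difference 13.20; 13.20 × −0.633 = −8.4.
- Mean 18: 20.30 against 5.80; difference 14.50; 14.50 × −0.633 = −9.2.

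Regression to the mean alone would thus show the sicker group improving by 8 to 9 points more. GOLD is only partly built from CAT, so this split is a stand-in for the mechanism, not a forecast for GOLD.

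**The case against.** **Redaction.** Part of SAP 5.1 is blacked out, including the word for what enters the models, and the content of SAP 11.3 is not readable. Protocol 9.7.2 is not readable either, although the ENCePP checklist cites it for covariates. A reader might infer that the association with change is never analysed. The documents do not support that; the supportable statement is that the readable text specifies no such analysis. The readable analyses of CAT change against another variable use adherence and willingness to continue (two SAP shells, both numbered 10.2.3), and 8.3 lists neither.

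**The primary result.** No objective in Protocol 8.2 concerns covariate associations, Protocol 9.5 tests no hypotheses, and SAP 11.2.1.1 promises only the mean change with its interval. This stands and limits the severity.

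**Adjustment.** A reader might infer that the covariate-adjusted footnotes are false. That goes too far. The identity with the raw change holds only for the linear model with complete data and covariates fixed at baseline. Protocol 9.5 expects 15% dropout, GOLD and smoking are followed at both visits, and the logistic model does change the visit odds ratio.

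**The column heading.** Table 6.2.1 is headed LS mean, so its covariate rows might be meant as mean change by covariate level. The shell is ambiguous. That reading does not help, however: without an interaction the linear model gives the same change at every level, and an LS mean by level is again a CAT level over both visits.

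**Invented effect sizes.** L and D come from no document. They illustrate the mechanism and do not predict the results.

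**Conclusion.** The point holds for the covariate question and should be fixed. On the readable text, the two models to which SAP 5.1 points cannot deliver the examination planned in 8.3, and two table shells would show differences in level, or in odds of CAT ≥ 10, under titles about change. With SD of change 9.0 and assumed visit SDs of 8/8 or 8/10, the covariate estimate was about 6 where the difference in change was 0, and 0.0 to 0.4 where it was −2. For scale, Protocol 9.5 expects an overall change of 1.0.

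A reader might infer that the primary estimate is biased. It is not biased by this defect: with complete data and baseline-valued covariates, the linear model's visit contrast is the raw paired mean change. The conclusion rests on reading the term list as main effects and on there being no relevant analysis in the redacted text.

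**What to change.** 1. Keep the visit contrast of SAP 11.2.1.1 as the primary estimate. State that baseline values of GOLD group and smoking are used.
2. For the 8.3 question, fit one additional model per CAT outcome with visit-by-baseline-covariate terms for age, sex, obesity, smoking and pack-years. Report each as the difference in CAT change, or as the ratio of visit odds ratios for CAT ≥ 10, with its 95% CI, labelled exploratory.
3. In Tables 6.2.1 and 7.2.1, label the existing covariate rows *difference in CAT level, both visits combined* and *odds ratio for CAT ≥ 10, both visits combined*, or remove them.
4. Do not interpret a visit-by-GOLD term as effect modification. Leave it out, or report it with a regression-to-the-mean caveat; Protocol 9.9 already names that effect.
5. If the redacted text already contains such an analysis, refer to it from 8.3 and 5.1; the labels in item 3 are still needed.

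The cost is SAP wording, one extra model run per outcome and two revised shells, with no new data. The downside is wider intervals, about ±1 CAT point for an evenly split covariate at N = 1310 and more for an uneven split, and several exploratory comparisons that need cautious reading.

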9. RESEARCH METHODS

9.1 STUDY DESIGN

This is a non-interventional, 3-months prospective, two visits, single-cohort, multicenter, nationwide study in patients with stable COPD who have been using maintenance therapy with tiotropium monotherapy (Spiriva® Handihaler®) for at least 3 months before, and for whom, according to their treating physician, a recent switch (within one week) to dual therapy with tiotropium bromide plus olodaterol (Spiolto® Respimat®) have been required, in the Greek private and public sector pulmonary offices and clinics.

In all cases, the decision to switch the treatment strategy from Spiriva® Handihaler® to Spiolto® Respimat® will be previous and completely independent from the initiation of this non-interventional study. Additionally, the decision of the treating physician will be according to the daily clinical practice in the corresponding center.

The intended Health Care Professionals (HCPs) are office-based pulmonologists and practice physicians from Hospital pulmonary clinics, who are treating symptomatic COPD patients every day, being aware that most of their patients suffer from the physical restrictions induced by the disease *per se*.

Enrolment of patients will not be competitive. Each investigator will recruit up to 10 eligible patients in a consecutive manner from those who come to control visits and have been using tiotropium administered with Spiriva® Handihaler® for at least 3 months before the decision to switch to a combination therapy with tiotropium bromide plus olodaterol administered with Spiolto® Respimat® has been made. The enrolment period will last for a maximum of 9 months. All centers will stop recruitment once the total sample size of 1500 patients is achieved or, alternatively, at the end of the 9-months planned period of enrolment.

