9.2 SETTING

It is planned that data of approximately 1500 COPD patients from approximately 150 sites (around 148 office-based pulmonologists and 2 Hospital pulmonary clinics) throughout Greece will be collected. Each investigator will recruit up to 10 eligible patients in a consecutive manner who have been using tiotropium administered with Spiriva® Handihaler® for at least 3 months before the decision to switch to a combination therapy with tiotropium bromide plus olodaterol administered with Spiolto® Respimat® has been made, according to the daily clinical practice in the corresponding site.

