9.5 STUDY SAMPLE SIZE

The sample size determination is not based on a power calculation because no hypotheses will be tested. The primary endpoint of change in score of COPD Assessment Test (CAT) within three months after the switch from Spiriva® Handihaler® to Spiolto® Respimat® will be analysed descriptively by mean and 95% confidence interval. From other studies a mean difference in CAT score of 1.0 and standard deviation of 9.0 are expected.

With a sample size of 1310, a two-sided 95% confidence interval for the difference in paired mean scores will have an interval that extends by no more than 0.5 from the observed difference in means (e.g. an interval from 0.5 to 1.5 for a difference of 1.0), with 90% coverage probability, assuming that the true standard deviation of differences is 9.0 and that the confidence interval is based on the t statistic. The calculation was performed using the MOC3 routine from commercial software nQuery Advisor® 7.0 (██████████ [R15-1331]). To account for a 15% dropout rate, 1507 patients will be needed. Therefore, it was decided to enroll 1500 patients in the study.

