### 10.3 Handling of Inconsistencies in Data and Outliers

To identify the possible outliers, Z-score and IQR (interquartile range) methods will be used. An observation will be considered as an outlier if it is not included in the following interval for the primary and secondary continuous variables: ( $Q_1 - 1.5 \times IQR$ ,  $Q_3 + 1.5 \times IQR$ ). In order to visualise the outliers, histograms and/or scatterplots will be generated with the rest of the data. If the effect of the outliers is strong, delete or replace will be examined.

Any removal or replace at the analysis will be documented, stating the site and patient number as well as the reason for removal.

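### The stated models for CAT, EQ-VAS and mMRC change, and the precision calculation, treat patients as independent across about 150 sites; if change varies between sites, the 95% intervals are too narrow.

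*SAP*

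**What the plan says.** **Sites.** Protocol 9.2 plans about 1500 patients from about 150 sites: "Each investigator will recruit up to 10 eligible patients in a consecutive manner". Ten is a cap. Under Protocol 9.1, recruitment ends when 1500 is reached "or, alternatively, at the end of the 9-months planned period of enrolment".

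**Sample size.** Protocol 9.5 tests no hypothesis. It asks for a two-sided 95% interval for the mean paired CAT difference that extends at most 0.5 either side, with 90% probability, "assuming that the true standard deviation of differences is 9.0 and that the confidence interval is based on the t statistic". This gives 1310 patients; after an allowance for 15% dropout, 1500 are enrolled. No ICC or design effect appears.

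**Models for change.** SAP 11.2.1.1 fits an MMRM with patients as random, an unstructured covariance ("allowing adjustment for correlations between study visits within the study patients") and Kenward-Roger degrees of freedom. Its covariates are: "Visit, GOLD group, smoking habits, packyears, sex, age, and comorbidities appearing at a rate greater than 5% will be entered as covariates". SAP 11.2.2.2 (EQ-VAS) and 11.2.2.9 (mMRC) use the same specification. Site is not mentioned. The list in SAP 8.3 is open ("The following variables will be considered, among others, as covariates") but does not name site either.

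**Models for odds ratios.** The CAT ≥10 analysis is a logistic GEE: "comorbidities appearing at a rate greater than 5% will be entered as covariates and unstructured covariance matrix will be used". The ordinal GEE in SAP 11.2.2.3 is worded alike. Neither names the clustering unit.

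**The concern.** Patients of one physician share that physician's prescribing habits, inhaler instruction and way of administering questionnaires. Site differences that are equal at both visits cancel from the change. Differences in the change itself do not, and they make patients within a site correlated. An interval that ignores this is too short.

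The documents name features that could differ by site: Respimat training (Protocol 9.7), urban and rural locations (9.2.2), and office and hospital settings (9.2). SAP 11.2.1.1 also assigns a CAT score of 40 after death, drop-out for an adverse event or treatment discontinuation. Any difference between sites in discontinuation therefore enters the change score directly.

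The study is descriptive, so its main result is a mean CAT change with a 95% interval. The validity of that interval is what is at stake.

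**Working it through.** **Inputs.** From Protocol 9.2 and 9.5: 150 sites, 1500 enrolled, 15% dropout, SD of change 9.0, target half-width 0.5, probability 90%. Assumed, because the documents are silent: ICC of change 0.01, 0.02, 0.05, 0.10.

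**1. The plan's own figure.** Find the smallest n with P(t(0.975, n−1)·s/√n ≤ 0.5) ≥ 0.90, where (n−1)s²/81 is chi-square with n−1 degrees of freedom. The result is n = 1310 (probability 0.9007), so Protocol 9.5 reproduces exactly. The formula assumes independent patients.

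**2. Patients analysed.** 1500 × 0.85 = 1275, and 1275/150 = 8.5 per site. The unadjusted half-width is 1.962 × 9/√1275 = 0.494.

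**3. What the stated MMRM estimates.** With two visits, complete pairs and covariates entered as main effects, a covariate shifts both visits equally and drops out of the change. The visit effect is then the mean paired difference, with its ordinary standard error. This holds for site too. In one simulated data set (1275 patients, 150 sites, ICC 0.05), the standard error of change was 0.2577 without covariates, 0.2577 with sex and age, and 0.2577 with 150 site indicators added. The site-clustered standard error was 0.310.

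**4. Effect of clustering.** The design effect is DE = 1 + (8.5 − 1) × ICC. Coverage of the unadjusted interval is 2Φ(1.96/√DE) − 1. The correct half-width is 0.494 × √DE.

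| Assumed ICC of change | DE | Coverage of nominal 95% CI | Correct half-width (CAT points) |
|---|---|---|---|
| 0.01 | 1.075 | 94.1% | 0.51 |
| 0.02 | 1.15 | 93.2% | 0.53 |
| 0.05 | 1.375 | 90.5% | 0.58 |
| 0.10 | 1.75 | 86.2% | 0.65 |

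For a given ICC, coverage does not depend on the SD, so that column also serves EQ-VAS and mMRC. The half-widths are for CAT only.

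**5. Simulation** (20000 runs, 150 sites of 8 or 9, normal site effect on change). Unadjusted coverage was 94.2, 93.4, 90.2 and 86.2%. With a site-clustered variance and 149 degrees of freedom it was 95.0, 95.2, 94.8 and 95.2%.

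**6. Missing Visit 2 values.** A two-visit likelihood model keeps patients who have only a baseline. It was simulated in 6000 runs with 1500 enrolled and 15% missing at random (assumed: baseline SD 7, baseline ICC 0.05, correlation of baseline with change −0.3). Model-based coverage was 93.4, 93.7, 90.4 and 86.1%. Site-clustered coverage was 94.2, 95.2, 95.0 and 95.3%.

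**7. Under-recruitment illustration.** If site sizes were uniform on 1 to 10, the mean would be 5.5 and the total 150 × 5.5 = 825. The size-weighted mean is 38.5/5.5 = 7.0, so DE = 1.06, 1.12, 1.30 and 1.60, and coverage is 94.3, 93.6, 91.4 and 87.9%. With 825 patients the half-width is already 1.963 × 9/√825 = 0.615 at ICC 0. The 0.5 target would then be missed through recruitment alone, so this is not a picture of the planned study.

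**The case against.** **The condition is not evidenced.** No passage gives or implies an ICC of change, and site differences at baseline cancel. This stands: the size of the problem rests on an assumption, and at 0.01–0.02 the loss is minor.

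**The effect in CAT points is modest.** The half-width grows by about 0.02 to 0.16 points on a 0–40 scale. For the expected change of 1.0, the interval would be about 0.42 to 1.58 at ICC 0.05 and 0.35 to 1.65 at 0.10, against 0.51 to 1.49 unadjusted. The reading of such a result would not reverse. This also stands, but an interval reported as 95% should have close to that coverage.

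**Redacted text may deal with site.** SAP 5.1 says that some redacted item enters the primary and first secondary models. The bases of Tables 6.2.1 to 6.2.3 are hidden, and so is SAP 11.3. A site-adjusted sensitivity analysis cannot be excluded, so a reader should not infer that the SAP contains none. The primary model's specification in SAP 11.2.1.1 is nevertheless legible, and a site covariate added as a main effect would cancel. That covariates carry no visit interaction is inferred from the SAP's silence, which is the natural reading.

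**The GEE models.** A reader might infer that the odds-ratio intervals are wrong too. The SAP does not name their clustering unit, which is an ambiguity and not a shown error. No coverage is claimed for them.

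**The sample size.** A reader might call Protocol 9.5 an error. It is a correct calculation under an independence assumption that it leaves unstated.

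**Conclusion.** The concern holds, conditionally. The precision calculation and the stated MMRMs for CAT, EQ-VAS and mMRC change make no allowance for between-site variation in change. If that variation exists, the 95% intervals are too narrow. With 8.5 analysed patients per site, coverage is about 93–94% at an ICC of 0.01–0.02, about 90.5% at 0.05 and about 86% at 0.10. The loss is small in the first range and material from about 0.05. At 0.05 the interval misses the true value about 9.5% of the time instead of 5%.

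The ICC is assumed throughout, and the conclusion is limited to the models that can be read. One might go on to infer a biased mean change; nothing here supports that, because what is affected is the width of the interval.

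**What to change.** In SAP 11.2, compute the 95% intervals for the CAT, EQ-VAS and mMRC changes with a site-clustered robust variance. Say explicitly that a site main effect or a random site intercept alone would not do this, because both cancel from the change. Report the ICC of change. State in the SAP or study report that the 0.5 precision in Protocol 9.5 assumes no between-site variation in change; no protocol amendment is needed for this.

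The cost is SAP wording and some programming. Site is already recorded: SAP 10.3 has removals documented "stating the site and patient number as well as the reason for removal". Kenward-Roger is given up for these intervals, and they become slightly wider even without clustering: at ICC 0 (1275 patients, SD 9) the simulated half-width is 0.497 instead of 0.494.

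A random site-by-visit effect in the MMRM is a possible alternative. It was checked only with an analysis-of-variance estimator on change scores and is untested within the full covariate-adjusted model. No change to the GEE working correlation is requested.
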